12.10.4. Statistical Analysis of Pharmacokinetic Data

No inferential statistical analysis of PK parameters will be conducted.

12.11. Pharmacokinetic/Pharmacodynamic Analysis

Additional population PK/PD analysis may be conducted in case of non-linear concentration-QTc relationship, large HR effect, or time delay between drug concentration and QTcF effect.

A detailed analysis plan of the primary C-QTc analysis will be prepared prospectively as a separate document (C-QTc analysis plan). It will include all technical details of the primary analysis modeling approach.

12.12. Analysis of Safety Data

Safety data (scheduled and unscheduled) will be presented in the data listings. Continuous variables will be summarised using descriptive statistics (n, mean, SD, minimum, median, maximum) by treatment. Changes (and/or percentage change) from baseline will be presented where applicable when baseline is defined. Categorical variables will be summarised in frequency tables (frequency and proportion) by treatment. The analysis of the safety variables will be based on the Safety Analysis Set.

Tabulations and listings of data for vital signs and clinical laboratory tests will be presented. Data will be summarised for the observed values at each scheduled assessment, together with the corresponding changes (and/or percentage change) from the baseline when baseline is defined. 12-lead safety ECG data will be listed only. Out-of-range values will be flagged in individual listings for safety laboratory findings, vital signs and 12-lead safety ECGs findings. Furthermore, out-of-range values will be summarised descriptively for safety laboratory findings and vital signs using agreed standard reference ranges and/or extended reference ranges (eg, AstraZeneca, program, or laboratory ranges).

12.12.1. 12-lead Safety Electrocardiogram

The 12-lead safety ECG results will be listed for each subject and out-of-range results will be flagged. Abnormal findings may be classified as AEs if considered clinically significant by the Investigator. See Section 13.2.6 for AE reporting.

12.12.2. Adverse Events

All AEs will be coded using MedDRA vocabulary and will be listed for each subject. Adverse events will be assigned to a treatment based on the start date/time of the AE in relation to dosing in that period; for tabulation purposes the AE will then be assigned to the treatment received in the respective treatment period as follows:

- Screening: all AEs with start date/time prior to dosing in Treatment Period 1 (from time of randomisation for AEs and from time of signed ICF for SAEs).
- Treatment Period 1: AEs with start date/time at the time of or after dosing in Treatment Period 1 until the time of dosing in Treatment Period 2.
- Treatment Period 2: AEs with start date/time at the time of or after dosing in Treatment Period 2 until the time of dosing in Treatment Period 3.
- Treatment Period 3: AEs with start date/time at the time of or after dosing in Treatment Period 3 until the final Follow-up Visit.

Adverse events with missing start dates/times will be handled as follows:

- If the start date is completely missing but the end date is known and shows that the AE ended on or after the first dose date, then the start date will be imputed as the first day of dosing; if the end date is known and shows that the AE ended before the first dose date, then the screening date will be used for the start date. If the end date is non-informative (ie, is missing or does not contain enough information), the start date will be imputed as the first date of dosing;
- If only the start day is missing the day will be imputed as the first day on which a dose was given in that month unless the end date is known and shows that the AE ended before a dose was given in that month; in which case the date will be imputed as 01. If the end date is non-informative (ie, is missing or does not contain enough information), the start date will be imputed as the first date of dosing in the known month. If the month is not a dosing month the date will be imputed as 01;
- If the start day and month are missing the date will be imputed as the first day of dosing in the known year unless the end date is known and shows that the AE ended before a dose was given in that year; in which case the start day and month will be imputed as 01Jan or with the date of screening if this is later. If the end date is non-informative (ie, is missing or does not contain enough information), the start date will be imputed as the first date of dosing in the known year. If the year is not a year of dosing, then the date will be imputed as 01Jan or with the date of screening if this is later.
- Missing times will be imputed as 00:00 h or with the time of dosing for events starting on a dosing day.

Adverse events will be summarised by treatment and overall for all subjects, including tabulations by causality and severity (mild, moderate and severe). All tabulations will be presented by SOC and PT.

All tabulations will include the number and percentage of subjects. In addition, a separate tabulation will be presented showing the number of events by treatment and PT.

Finally, an overview of all AEs will be presented, separately for the number and percentage of subjects and the number of events. This will include categories for any AE, SAEs, AEs leading to discontinuation of IMP (DAE) and AEs with outcome of death.

Listings of all AEs, SAEs, DAEs and AEs with outcome of death will be presented. Adverse events that occur before dosing will be presented separately.

The following information will be included in the listings: verbatim term, SOC, PT and lowest level term, start date/time, end date/time, time from last dose, causality, action taken, whether the AE was classified as serious and the outcome.

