13.2.3. Variables

The following variables will be collected for each AE:

- Adverse event diagnosis/description
- The date and time when the AE started and stopped
- Maximum intensity
- Whether the AE is serious or not
- Investigator causality rating against the IMP (yes or no)
- AE caused subject's withdrawal from study (yes or no)
- Outcome

In addition, the following variables will be collected for SAEs:

- Date AE met criteria for serious AE
- Date Investigator became aware of serious AE
- AE is serious due to

- Date of hospitalisation
- Date of discharge
- Probable cause of death
- Date of death
- Autopsy performed
- Causality assessment in relation to study procedure(s)
- Causality assessment to other medication

The following intensity ratings will be used:

- 1 Mild (awareness of sign or symptom, but easily tolerated)
- 2 Moderate (discomfort sufficient to cause interference with normal activities)
- 3 Severe (incapacitating, with inability to perform normal activities)

It is important to distinguish between serious and severe AEs:

- Severity is a measure of intensity whereas seriousness is defined by the criteria in Section 13.1.2.
- An AE of severe intensity need not necessarily be considered serious. For example, nausea that persists for several hours may be considered severe nausea, but not a SAE. On the other hand, a stroke that results in only a limited degree of disability may be considered a mild stroke but would be an SAE.

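### An AE kept as one record takes its treatment from its start and its severity from its peak, so a symptom that worsens after a later dose can be tabulated under the wrong treatment, or under none

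*Combined protocol and SAP*

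**What the plan says.** Section 12.12.2 assigns treatment by onset: "Adverse events will be assigned to a treatment based on the start date/time of the AE in relation to dosing in that period". The windows run from one dose to the next. The first, for example, covers "AEs with start date/time at the time of or after dosing in Treatment Period 1 until the time of dosing in Treatment Period 2", so the wash-out belongs to the earlier treatment. Anything starting before the first dose goes to a Screening category, and "Adverse events that occur before dosing will be presented separately".

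Section 13.2.3 lists what is collected for each AE. For severity the item is "Maximum intensity", and for causality it is one yes/no rating. No date of a change in intensity is collected.

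Section 12.12.2 then tabulates AEs by treatment, including by causality and by severity. Its listing content includes "start date/time, end date/time, time from last dose, causality, action taken, whether the AE was classified as serious and the outcome"; intensity is not named.

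**The concern.** In a cross-over, the onset and the peak of one AE can fall under different treatments. The plan takes the treatment column from the onset and the severity from the peak, and tabulates the two as if they belonged together. Causality has the same weakness: a yes prompted by worsening after a later dose is reported under the earlier treatment.

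This does not depend on missing dates. The imputation rules in 12.12.2 do not touch it, and it arises when every date and time is known. If the time of worsening is not captured at data entry, it cannot be recovered at analysis.

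At stake is the by-treatment AE summary, which serves the secondary objective on safety and tolerability (section 6.2). With 24 subjects, one misplaced case is visible in a table where severe events should be few.

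**Working it through.** The plan gives no figure for this point, so there is none to reproduce. The check applies the written rule to worked records, counts the transitions, and then sizes the problem under stated assumptions.

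**1. Worked records, all dates known, one record per AE**

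- *Sequence CAB.* A mild symptom starts after placebo in Period 1, is ongoing, and becomes severe after Treatment A in Period 2. As written: placebo, severe; nothing under A. If the worsening were dated: placebo, mild; A, severe.
- *Other placebo-to-active sequences.* The same happens in BCA (the later treatment is A) and in ACB and CBA (the later treatment is B).
- *Pre-dose onset.* A mild symptom starts between randomisation (the evening before first dosing, section 9.9.1) and the first dose, then worsens after dosing. As written: Screening category, presented separately, in no treatment column.

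**2. Transitions** (six sequences from section 9.9.2; 24 subjects, 4 per sequence if balanced, which is an assumption)

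| Transition | Sequences | Subjects | Misplaced severity is credited to |
|---|---|---|---|
| Placebo to active | BCA, CAB, ACB, CBA | 4 × 4 = 16 | placebo |
| Active to placebo | ABC, BCA, ACB, BAC | 4 × 4 = 16 | active |
| Active to active | ABC, CAB, BAC, CBA | 4 × 4 = 16 | the other active treatment |

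The total is 48 = 24 × 2. For pre-dose onset, each of A, B and C is the first treatment in 2 of 6 sequences (8 subjects each), so the loss can fall on any column.

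**3. Expected number.** The documents give none of these rates. Assumed: 0.15 to 0.30 AEs per subject-period; 5% to 20% of them still ongoing at the next dose; 10% to 30% of those worsening after it.

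Expected cases = transitions × AE rate × P(ongoing) × P(worsens); P(at least one) = 1 − exp(−expected).

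- Placebo to active, low: 16 × 0.15 × 0.05 × 0.10 = 0.012, so 1.2%.
- Placebo to active, high: 16 × 0.30 × 0.20 × 0.30 = 0.288, so 25%.
- All transitions, low: 48 × 0.15 × 0.05 × 0.10 = 0.036, so 3.5%.
- All transitions, high: 48 × 0.30 × 0.20 × 0.30 = 0.864, so 58%.

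These count worsening of any grade. Pre-dose onsets are not included.

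**4. Size of one case.** 1/24 = 4.2 percentage points; with 20 subjects, 1/20 = 5.0.

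**The case against.** **Other sections treat worsening as reportable.** Section 10.4.4.1 requires a clinically relevant worsening of an ECG finding to be recorded as an AE. Sections 12.12.5 and 13.2.6 do the same for aggravated physical-examination findings, and 13.2.6 covers clinically significant deterioration in laboratory values and vital signs. Laboratory and vital-sign baselines are also reset each period (12.12.3, 12.12.4), with change and shift tables by treatment. This stands. It would be wrong to infer that the protocol never calls for a worsening to be reported as an AE. What remains is mainly symptom-type AEs. For these, section 13.1.1 says only that an AE may include a deterioration, which is a definition and not an instruction to open a new record.

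**The rule may exist elsewhere.** Appendix A (additional safety information) and the data-entry instructions were not in the text available for this review. A field for maximum intensity does not itself say when a new record is opened. This also stands: the consequence holds for an AE kept as one record.

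**Severe cases will be very rare.** Section 5.2.1.4 reports only 2 AEs above Grade 2 among 293 subjects in the pooled Phase I studies, one of them a creatinine increase. All on-treatment AEs in the later study were mild. The AE must also last to the next dose, at least 7 days after the previous one (5.3.2). This limits frequency, but does not remove the fault in the rule.

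**Nothing safety-critical depends on the table.** The withdrawal and hold rules (8.1, 8.1.1) do not use the table column, and the listed dates show that an AE spans two doses. True, but they do not show when it became severe.

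**A tempting stronger reading** is that the rule biases the active-placebo comparison towards no difference. The documents do not support it. Active-to-placebo transitions are as many as placebo-to-active ones and err the other way; active-to-active ones blur A against B. A net shift would require worsening that is itself caused by the drug, for which the documents give no figure.

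**Conclusion.** The concern holds in a limited form. For a symptom-type AE kept as one record across a dose, sections 12.12.2 and 13.2.3 together place peak severity and causality under the earlier treatment, or outside the treatment columns if onset was before the first dose. This follows from the stated rule and is not merely missing detail.

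The size is small. On the assumed rates the placebo-to-active case has about a 1% to 25% chance of occurring at least once. A reader might quote 4% to 58% instead, but that range covers all 48 transitions, two thirds of which cannot credit an active-treatment worsening to placebo. Neither range is limited to worsening to severe. Both rest on assumed rates and balanced sequences, and a recording rule in Appendix A could close the gap.

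Only the descriptive AE tables are affected; no inferential AE comparison is planned. This is a cheap improvement, best made before data entry begins.

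**What to change.** State in 13.2.3 and 12.12.2 that when an ongoing AE increases in intensity after a later dose, or a pre-dose AE does so after the first dose, the increase is recorded with its date and time. Two forms would work:

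- a new AE record linked to the first, starting at the worsening; or
- a dated intensity change within the same record, with maximum intensity tabulated within each treatment period.

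In either form, tabulate the worsened intensity and its causality rating under the treatment received in that period. Add intensity to the AE listing. If Appendix A already contains such a recording rule, cross-refer to it from 12.12.2 and align the tabulation rule with it.

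The cost is a sentence or two in each section, a data-entry instruction and slightly more data entry. With new records, a worsening AE counts twice in the number-of-events table and the first record's duration is cut short. Dated intensity changes avoid both, but need an extra field.

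### AEs with a completely missing or year-only start date default to the Period 1 treatment, and those missing only the day default to the first dose of the month; in this cross-over both rules can tabulate an AE under the wrong treatment

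*Combined protocol and SAP*

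**What the plan says.** Section 12.12.2 links each AE to a treatment through its start: "Adverse events will be assigned to a treatment based on the start date/time of the AE in relation to dosing in that period", and "for tabulation purposes the AE will then be assigned to the treatment received in the respective treatment period". Period 1, for example, takes "AEs with start date/time at the time of or after dosing in Treatment Period 1 until the time of dosing in Treatment Period 2".

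The same section then fills in missing start dates:

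- **Completely missing.** Where a known end date "shows that the AE ended on or after the first dose date, then the start date will be imputed as the first day of dosing". Where it instead "shows that the AE ended before the first dose date, then the screening date will be used for the start date". With a non-informative end date, "the start date will be imputed as the first date of dosing".
- **Only the day missing.** In general "the day will be imputed as the first day on which a dose was given in that month". Day 01 is used instead if the AE ended before a dose in that month, or if the month has no dose.
- **Day and month missing.** In general "the date will be imputed as the first day of dosing in the known year", with exceptions if the AE ended before dosing or the year is not a dosing year.

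Apart from separating events that ended before a dose, none of these rules uses the treatment period in which the AE was recorded. Section 12.1 commits to a separate plan only for the primary concentration-QT analysis and leaves all other analyses to the protocol, so no other document is committed to changing the rule.

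**The concern.** Imputing to the first dose is harmless where a subject has one treatment. Here each subject receives A, B and C in turn, so the imputed date selects the treatment. An event first recorded after the Period 3 dose, with no start date, is counted under whatever was given in Period 1.

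Safety and tolerability is a secondary objective (Section 6.2), and AEs are tabulated by treatment, causality and severity. With 24 subjects, one subject is 1/24 = 4.2% of a column, so a single misplaced event is visible. This is a stated rule that gives a wrong result, not a detail left for later.

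**Working it through.** The plan gives no figure to reproduce, so the check applies its rules directly. Each subject gets each treatment once, so a wrong period always means a wrong treatment.

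**Inputs from the protocol.** Six sequences, ABC, BCA, CAB, ACB, BAC and CBA (Section 9.9.2). Doses at least 7 days apart and follow-up 7 to 10 days after the last dose (Section 5.3.2). Planned dates June to September 2020 (Synopsis).

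**Assumptions.** Onset uniform over days from first dose to follow-up; non-informative end date; spacing of 7, 10 or 14 days.

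**Step 1: dates that default to Period 1.** This covers completely missing starts and, with all dosing in 2020, year-only starts. Six sequences × 3 true periods = 18 cells. The assigned treatment is always the Period 1 treatment, so 6 cells are right and 12/18 = 67% are wrong. The 12 wrong cells split as follows:

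- 4 from one active treatment to the other;
- 4 from active to placebo;
- 4 from placebo to active.

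In calendar days, with spacing g and follow-up f, there are 2g + f + 1 possible onset days, of which g lie in Period 1. The wrong share is (g + f + 1)/(2g + f + 1).

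**Step 2: only the day missing.** Two examples at 7-day spacing with follow-up at 7 days (22 onset days):

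- Doses on 3, 10 and 17 June. Any June start becomes 3 June (Period 1). Onsets on 10 to 24 June are wrong: 15/22 = 68%.
- Doses on 25 June, 2 July and 9 July. A June start becomes 25 June, which is right for all 6 June days. A July start becomes 2 July (Period 2). That is wrong for 1 July (truly Period 1) and for 9 to 16 July (truly Period 3): 9/22 = 41%.

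**Step 3: all dosing dates.** The rules were applied to every Period 1 dosing date from 1 June 2020 that allows follow-up by 30 September 2020.

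| Spacing / follow-up (days) | Dosing dates | All three doses in one month | Wrong: missing or year-only | Wrong: day only missing | Day only missing: assigned to Period 1 / 2 / 3 |
|---|---|---|---|---|---|
| 7 / 7 | 101 | 59 (58%) | 15/22 = 68% | 53% | 69% / 17% / 14% |
| 7 / 10 | 98 | 56 (57%) | 18/25 = 72% | 52% | 63% / 18% / 19% |
| 10 / 10 | 92 | 32 (35%) | 21/31 = 68% | 45% | 51% / 27% / 22% |
| 14 / 10 | 84 | 8 (10%) | 25/39 = 64% | 38% | 43% / 30% / 26% |

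Day-only errors run both ways: 3% to 6% of all such AEs began in Period 1 but are assigned to Period 2.

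**Step 4: an imputed start after the event was recorded.** Take doses on 20 June and 10 July. An AE is recorded on 9 July (Day -1 of Period 2) with start July, and is ongoing. Its end date is non-informative, so the start becomes 10 July. That is the day after it was recorded, under a treatment not yet given.

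**Step 5: information already held.** Table 5-2 schedules AE questioning on Day -1, pre-dose, and at 4, 12, 24 and 48 hours in each period, and again at follow-up. The standard question in Section 13.2.5 covers the time since the subject was last asked. Because one questioning falls just before each dose, the visit at which an AE is first recorded normally identifies its period.

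**The case against.** The strongest reply is that the rule will rarely be used. Start date and time are collected for every AE (Section 13.2.3), questioning is frequent, missing data go to the Investigator (Section 11.4.1), and queries repeat until no discrepancies remain (Section 11.5). AE tables are descriptive, every AE is listed individually, and the primary QTcF analysis is untouched. All of this stands. It limits the size of the problem, but it does not make the rule right when it is used.

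It is also fair to say that the rules do consult the end date. They do so only to separate events that ended before a dose from the rest. An end date in Period 3 does not prove onset in Period 3, so the end date alone would not settle the period.

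Two stronger readings are tempting, and the documents support neither.

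- **Every partial date goes to Period 1.** When only the day is missing, the rule uses the first dose in the known month, which can be the Period 2 or 3 dose, or day 01. The 2/3 figure therefore covers only dates that default to Period 1.
- **The rule moves events from active treatment to placebo.** Four cells move that way, but four move from placebo to active. With six balanced sequences the expected effect is dilution, not a shift. Dilution is still unwelcome in a safety comparison, because it pulls a real difference towards none.

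**Conclusion.** The point holds in a limited form. A completely missing start (unless the AE ended before the first dose), or a year-only start with all dosing in one year, is tabulated under the Period 1 treatment whatever period it was recorded in. About 2/3 of such events get the wrong treatment if onset is equally likely in each period; the range is 64% to 72% when onset is spread evenly over days. When only the day is missing, about 38% to 53% are wrong at 14- to 7-day spacing, given uniform onset and a non-informative end date, and the imputed start can fall after the event was recorded.

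These are shares of affected events. The documents do not say how many AEs will lack dates, and the number is probably small. The consequence is diluted treatment differences in the AE tables, with no systematic advantage to one treatment. It is worth correcting because the correction is cheap.

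**What to change.** Replace the first-dose rules in Section 12.12.2 with imputation inside the treatment period of the AE questioning at which the event was first recorded. The start is set to the most recent dose before that questioning, bounded by the previous questioning, any known month or year, and any known end date. Flag imputed starts in the listing.

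If the period still cannot be determined, show the event under each possible treatment in a sensitivity table. A default to an active treatment would be no better: it is itself a systematic misassignment, and it does not say which active treatment when the subject has received both.

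The cost is a paragraph of wording, minor programming, and linking each AE to its questioning visit in ClinBase. The link needs attention because Section 13.2.3 lists an Investigator awareness date for serious AEs only and no report date for other AEs. No new assessment of subjects is needed.
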